4.1. Sampling

Communities: We selected by convenience two communities in Los Angeles (Hollywood and South Los Angeles) with large, low-income, mainly minority populations, where we have strong existing partnerships.

The **County of Los Angeles**, with nearly 10 million people, is one of the most populous and diverse counties in the United States: of the population, 43.9% are Latino, 33.5% white, 12.3% Asian, 10% Black and 0.3% American Indian. Over 20% live below the federal poverty level¹²⁸ with ethnic minorities over-represented among the poor. **South Los Angeles** has a population of about 1.5 million, with 60% Hispanic, 35% African American, 3% non-Hispanic White and 2% Asian American. The communities of South Los Angeles suffer from some of the highest rate of morbidity and mortality and the lowest rate of educational attainment, family income and insurance coverage in Los Angeles County.¹²⁸ **Hollywood-Metro** has a population of almost half a million: 60% Hispanic, 3% African American, 17% non-Hispanic White and 17.3% Asian American. Over half are foreign born and less than half have a high school diploma. A little over a quarter live in poverty and the median household income is 25% less than the county as a whole.¹²⁹ This area has the highest uninsured rates and highest percentages of adults and children with no regular source of care.¹³⁰

Agencies: The agencies to be included in the study will be those who participated in the Community Partnership Initiative and their partners.¹³¹ The CPI frame of 94 organizations, which was developed through publicly available, comprehensive lists of services agencies in Los Angeles County coupled with recommendations from lead community partners, included mental health, substance abuse, primary care, social service, and homeless and other community

agencies. Other agencies participated in the community feedback conference and expressed interest in further activities. We will invite agencies to participate through letters and phone calls and ask them to complete a web survey, review a description of the study, and suggest additional partners. Each consenting agency will provide a list of their sites or ‘units’ that provide services to adults and have at least one full-time equivalent clinician or case worker. Agencies will be enrolled in a rolling fashion over six months, grouped into two main batches, one for each area. We will recruit clinicians from this pool of units and finalize unit selection at the conclusion of agency/clinician enrollment by month 13.

(NOTE: With community input in the design period, the definition of agencies was expanded to include homeless-serving, prisoner re-entry and “community-trusted locations, including parks and recreation centers, senior citizen centers, faith-based programs, hair salons, and exercise clubs. In addition, to incorporate community priorities for vulnerable populations into account, each community was invited to nominate two vulnerable groups for over-sampling. South Los Angeles selected substance abuse agencies and neighborhoods with high concentration of African Americans. Hollywood-Metro selected homeless clients and senior citizens.)

Units or Programs: Sampling will be carried out with sites or autonomous divisions within sites as the units to be sampled. We expect to identify at least 100-150, with some agencies having over 10-15 units while others have one. We may divide large primary care and mental health specialty clinics into teams as the units. We will stratify units by agency type and randomly select within strata to obtain a sample of unit sample that is 30-40% primary care, 30-40% social service, and 20-30% mental health units that serve more “general community” populations, such as CalWorks contract agencies. In this way, we anticipate having at least 10 units from each category to facilitate fitting statistical models. We will attempt to enroll about 20-30% more units than needed, to allow for withdrawal/attrition. We will include those units in the administrator/clinician surveys even if not selected for the main trial to track spill-over of intervention activities or parallel types of program exposure from the market. Social service agencies are included to participate in screening, education, referral, and case management. Primary care settings can play roles in screening, assessment, case management, and treatment. Mental health specialty clinics provide treatment, consultation and supervision, and some units may participate in screening. We will replace units with others in the same stratum as needed. Units are the “unit of randomization” for this study. We will enroll units in batches (groups of

units) with “batch” as a blocking factor, randomizing units within batches to intervention or control.

Administrators: Each participating agency will identify a lead administrator. Some agencies will have a second administrator if they have units assigned to both study conditions. Administrators in all agencies will be asked to complete web-surveys at baseline and 12-18 months. They will be asked to facilitate agency participation in the intervention study and conferences.

Case Workers and Clinicians: Using lists of providers/case workers serving adults in participating units in the main study, we will randomly select up to 5 full-time case workers or clinicians per unit; but we will allow part-time (at least 50%) clinicians if necessary. We will provide them with recruitment packets, followed by phone calls or site visits. We will randomly select from the remainder in the same site/agency to replace refusers/drop-outs. *(NOTE: With community input, the definition of “provider” was expanded to all staff with direct client contact, including volunteers. We offered an invitation to all such staff to participate if they wished. In addition, we permitted staff of participating programs to participate in intervention activities, whether or not they enrolled as providers in the study).* Consenting providers will be asked to complete baseline and follow-up web surveys at 18 months and to participate in implementation for PIC/WE Care, depending on their intervention assignment. In PIC, 2 providers declined participation, and over 90% participated in 18-month surveys. Providers will learn of their unit’s participation status by letter before the Kick-off Conference for their community. We expect to have 175-225 case workers and providers in the main trial *(Note: expanded with expansion of the overall study to 250-300).*

Clients: In social service, community-based, and primary care units selected for the main trial, we will advertise the study with posters and fliers. On designated screening days, clinic staff will invite a consecutive sample of adult clients (over 18) visiting participating clinicians to discuss study participation with RAND field staff. *(Note: With community input, community members were hired and supervised by RAND).* Screening will occur over a one-month period for each unit. We expect 6,000 adult clients to be approached and 4,200 to complete screener surveys. Those over 18 with a positive depression score will be asked to enroll and complete a baseline interview that day or by follow-up telephone call and to participate in a 6-month telephone survey. Clients who do not speak English or Spanish, or who are too confused or agitated to complete the screener will be excluded.

Sample size: We expect 20% of clients to be eligible, due to the low-income of the communities. Some of the community agencies at the CPI feedback conference reported that 75% of their population had mild to moderate depression. Of 840 depressed adults, we expect 70% to enroll and complete baseline (588), 500 (85%) to complete 6-month, and 470 (80%) to complete 12-month follow-up, based on PIC experience.

(NOTE: Client screening protocols were changed in several ways. First, because the type of programs was expanded to include homeless-serving programs and other programs for vulnerable populations that did not necessarily have traditional ‘waiting rooms’ we also planned to screen at events such as food lines, but for those locations used a random selection rather than consecutive selection strategy. Second, all client targets were increased by more than 30% for the expanded sample for employment analyses and to compensate for lower follow-up retention rates due to inclusion of homeless clients. However, because depression rates were much higher on average than expected (18-50% depending on the sector) and because acceptance of screener and study enrollment offer was higher than expected (greater than 90%), we were able to use the same expected number of completed screener surveys to achieve both the necessary increases in enrollment and analytic sample for the expanded study.)

4.2. Intervention Assignment

Within each community and stratified by type of agency, we will randomly assign, using a computerized random number generator, the intervention conditions (community engagement implementation or low-intensity control dissemination) to the 50-60 units (programs) for screening clients. We will randomize additional units only providing implementation support (and not supporting client screening) to the two conditions. Within large networks (e.g., QueensCare), we may assign common conditions to collaborating units to maintain network ties. We will consider randomizing units that are matched based on program size and client sociodemographics, to improve client comparability by intervention status, as in PIC.¹³² Agency administrators and participating clinicians will be informed of their intervention status by letter.

(NOTE: Because of the large number of programs to be recruited, and the very diverse type of sectors recruited, and not all sectors had available up-to-date county lists, we decided to determine program eligibility in stages, in order to randomize a set of probable final programs, after which we planned to conduct site visits to determine final eligibility and final agreement of programs to participate.)

Programs will be informed of their intervention assignment status by a letter to their administrator after their enrollment is finalized. Recruiters of programs, administrators and providers are blinded to program intervention status until program recruitment is finalized. During recruitment, the study Principal Investigator will have access to intervention assignment information on a “need-to-know” basis (such as to answer questions from programs with recruitment finalized and notified of intervention status). Providers will be notified of program assignment through their program administrators. Clients will not be directly notified of their program’s intervention status by the study, but could be notified by their program’s administrator or providers. Survey staff for baseline and follow-up status will be blinded to program intervention assignment status.

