Overview: The primary goal in this group-level randomized trial is to estimate the difference in effects on outcomes, between intervention arms (e.g., CE condition vs. low-intensity control). To test our main hypotheses (that CEP would be more effective than RS in improving client health outcomes and addressing community priorities for housing and employment, while likely increasing services utilization), we will conduct intent-to-treat, comparative effectiveness analyses using intervention status as the independent variable. We will estimate logistic regression models for indicator variables and loglinear models for counts. Consistent with recommendations for group-level trials, (8) main models will incorporate adjustment for baseline status of dependent variables and covariates: age, sex, ≥ 3 chronic conditions, education, race/ethnicity, family poverty, 12-month alcohol abuse or illicit drug use, 12-month depressive disorder, and community. We will weight data for clients with baseline or six-month data to characteristics of eligible clients. For missing data, we will use item-level ^{155, 168} and wave-level ¹⁶⁹ imputation. Estimates and p-values are calculated using SUDAAN (<http://www.rti.org/sudaan/>) taking into account clustering within programs and weighting. We supplement findings from adjusted models with results from raw data to assess robustness. We will use two-sided tests with $p < .05$ for statistical significance.

We will also explore as an alternative approach multi-level models (also known as hierarchical models or random coefficient models) to account for the multilevel data structure with clients nested within units (agencies or relatively autonomous subdivisions thereof), and repeated measurements nested within clients.¹⁷⁰⁻¹⁷³ For this approach, we will apply two-level models for the cross-sectional data with clients nested within units; and three-level models for the longitudinal data with repeated measurements nested within clients and clients nested within units. To perform multilevel analyses, we will use special software such as the MIXED and GLIMMIX procedures in the SAS System V9, HLM6,¹⁷⁰ MLWin¹⁵⁹, Mplus¹⁷⁴ tailored for these analyses.

Two-level model for cross-sectional data analysis The statistical model for a “cross-sectional” analysis with one observation per client, for example Y =satisfaction at 6 months follow-up, is presented via two regression equations:

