In group-level randomized trials design such as PIC and CPIC, the power analysis is complex because there are many factors that influence power^{176, 177}. For a simple group-level randomized trial, the power of a test such as a t-test in comparing two group means is a function of the cluster size (m), the number of clusters (J), and the intra-class correlation (ICC), the ratio of the between-cluster variability between clusters to the total variability. In our application where cluster is organization unit, we use Kish's method^{176, 177} to adjust the standard errors by the variance inflation factor (VIF) defined as $VIF=1+(m-1)\times ICC$, where ICC is the intra-class correlation at the organization unit level. For analysis of repeated measures, we use an extended formula accounting for inter-temporal correlations within individuals and within units¹⁷⁷. Based on PIC data, outcome analyses on depression care and clinic outcomes have shown that the ICC at the clinic level is either absent or around 0.01, and inter-temporal correlation coefficients within individuals and within units over a 12-month time period are greater than 0.60. PIC provider data shows that ICCs are nearly absent for provider experience and around 0.00-0.05 for knowledge. Taking a conservative approach, we assume that ICC at the unit level ranges from 0.00 to 0.02 for client data and from 0.00 to 0.05 for provider data, and that the inter-temporal correlation is 0.50. In the calculation of power for testing intervention effects from a t-test, we use degrees of freedom equal to (number of clusters – 2) when $ICC>0$, which is conservative for assessing significance, although we also explore setting degrees of freedom equal to $N-2$ (N =total sample size) for the scenario where $ICC=0$ (the optimistic scenario). We also note that regression analyses adjusting for baseline covariates and stratification variables can improve statistical power if covariates explain a substantial portion of the uncertainty.¹⁷⁷ All power analyses are conducted with power of 80% or above as adequate, assuming two-sided tests with significance level 0.05. For client data, we provide detailed power analysis for two primary study variables (appropriate depression care and probable depression).

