Our initial power analyses were based on assumptions about effect sizes derived from prior studies of primary care patients, including ethnic minority patients, and that the main intervention effect would be related to increasing rates of treatments for depression. During the partnered design year, as the community leaders requested inclusion of especially vulnerable populations and services sectors for inclusion expanded, for example to faith-based agencies, senior centers, homeless-serving providers, and prisoner-reentry programs, and outcomes were added such employment, we revisited our estimates of power. First, to accommodate the interest

in employment outcomes we submitted a supplemental grant application which was funded, allowing some expansion in sample. However, even after this point, the focus on homelessness and homeless outcomes emerged in planning. This raised several scientific and operations issues, including that we might have greater attrition than planned, necessitating a larger enrolled sample, and that effect sizes might not be as large as planned, because of the greater difficulty in improving outcomes in complex populations. We therefore decided to assume that we needed approximately an increase in enrolled sample relative to our proposed sample for adequate power under more conventional conditions for fielding quality improvement interventions. These adjustments are given in the Table 3 below, including power for originally proposed sample based on prior primary care studies; power for the analysis of the same sample to address employment; and then based on revised assumptions, prior to any recruitment, to capture smaller effect sizes expected for a more clinically and socially vulnerable sample with potentially higher attrition rates. After the participatory design phase, the final study was designed to have a power of .80 with an alpha of .05 (two-sided) and ICC=.00-.02^{176, 177} to detect group difference of 10% to 11% or higher in comparing two proportions and standardized effects size of .20-.22 or higher in comparing two means. Enrolling 557-600 participants per condition (1114-1200 in total) allowed a retention rate of 65-70% at 6 month follow-up.

Table 4. Minimum detectable effect sizes for main analyses (80% power (alpha=0.05), two-sided test)*			
Note	Analytic sample size at 6 months follow-up	Effect Size†	Point Change§
Original grant	500	0.25-0.27	12.43-13.18%
With 30% expansion	650	0.22-0.24	10.92-11.78%

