With further 20% expansion, final	780	0.20-0.22	9.98-10.92%

†Detectable effect size (mean difference between two groups divided by the standard deviation)¹⁷⁸. §Detectable percentage point difference for two groups.

6. CPIC 3-Year extension (PCORI award # 1845)

Background: Depression is a leading cause of morbidity with disparities in care. Depression collaborative care, a team-based approach supporting care management, patient activation and evidence-based treatments, is effective relative to usual care but often unavailable in under-resourced communities. Community Partners in Care (CPIC) randomized 95 programs in healthcare and community-based (e.g., social services, faith-based) service sectors in two communities to Resources for Services (RS) for individual program technical assistance versus

Community Engagement and Planning (CEP) for multi-sector coalition support for depression collaborative care. For depressed clients, CEP relative to RS reduced having poor mental health-related quality of life (MHRQL) and behavioral health hospitalization over 6-12 months. Longer-term outcomes are unknown.

Aims: This extension study of CPIC aims to:

1. Compare CEP and RS effects at 3-year follow-up, 2-years after intervention support, on primary (depression and MHRQL), community-prioritized outcomes of physical health-related quality of life (PHRQL) and behavioral health hospitalization, and outpatient services use (secondary);
2. Compare effects of CEP and RS at 6, 12, and 36 months for CPIC participants enrolled in healthcare or community-based service sectors;
3. Describe outcome priorities for African American and Latino depressed clients, and as perceived by providers.
4. Describe views of stakeholders planning the Los Angeles County Health Neighborhood Initiative (HNI) informed by CPIC; and national stakeholders briefed on CPIC and HNI.

We hypothesized that CEP relative to RS would improve long-term mental and physical health and reduce hospitalization nights, overall and within sector. We expected stakeholders to prioritize social factors and mental health.

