All 80 participating CPIC agencies will be asked to identify service locations in the community areas, for which they have at least one full-time equivalent clinicians/case workers that serve adults; and to provide the number of eligible clinicians or case workers in those locations. These units will be the focus of clinician recruitment (see below). We expect most participating agencies to have 1-4 eligible units, but some will have more than 10. We will explore the feasibility of splitting some units into distinct teams. We expect to identify 150-200 eligible units across agencies.

All participating agencies' eligible units (150-200) will be considered for selection into the main trial. We will select a stratified sample, by agency type, to achieve 50-60 participating units (25-30 per community) for the main study, but expect to have another 25-30 participate in the ongoing administrator and clinician surveys but not in the main study.

Among the participating organizational units, we will randomly assign them (stratified by community and type of agency) to participation in the 2 study conditions; for very large, well-

established, multi-agency networks (such as QueensCare), we may randomize units within that network to preserve network ties. Agencies and organizational units will be informed of their randomization status by letter prior to the study's Phase 1 Kick-Off Conference. Some agencies may have units in both Phase 1 intervention conditions in the trial, and for this purpose, will identify a lead administrator for that agency for each intervention condition, and ask the additional administrator to complete the baseline administrator survey. This will increase the administrator pool across the 80 CPIC agencies to about 100.

All agencies will be asked to commit to participate in the administrator/agency web surveys, clinician surveys, and Feedback Conference. Agencies selected for the main trial will be asked to send 1-2 representatives to a Kick-Off Conference in their community, participate in the relevant intervention planning and implementation activities for each condition, and participate in a client outcomes study. Intervention agencies will be asked to assist training for the controls in the wait-list training after the main trial.

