For all study components (including supplement components discussed below), we convened working groups co-chaired by academic and community members to review analysis plans, data output and discuss findings.

Analyses for 6-month outcome: We conducted intent-to-treat, comparative-effectiveness analyses with intervention status as the independent variable, using logistic regression for dichotomous measures and Poisson regression models for count variables. Covariates were selected to account for known associations of sociodemographic and clinical status indicators with primary outcome measures. We adjusted for baseline status of dependent variables and covariates (age, sex, ≥ 3 chronic general medical conditions from a list of 18, education, race/ethnicity, family income < federal poverty level, 12-month alcohol abuse or use of illicit drugs at baseline, 12-month depressive disorder at baseline, and community). All analyses were conducted using SUDAAN Version 10.0 (<http://www.rti.org/sudaan/>) and accounted for clustering (clients within programs), weighting, and multiple imputations. Significance of comparisons by intervention status was based on regression coefficients. Results of logistic regression models are presented as odds ratios (OR) and Poisson models as rate ratios (RR) with 95 % confidence intervals. We illustrate results for intervention groups adjusted for covariates using standardized predictions generated from fitted regression models.¹⁴ We present Cohen's effect size index h , defined for dichotomous variables,¹⁵ where $h=0.20$ is small, $h=0.50$ is medium and $h=0.80$ is large. We supplement adjusted models with unadjusted raw data to assess

robustness. We applied a Bonferroni adjustment considering two primary outcomes (Poor mental health qualify of life $MCS-12 \leq 40$, and at least mild depression $PHQ-9 \geq 10$) and compared the proportion of results across outcomes favoring one intervention to an assumed null-hypothesis of 0.5.

Analyses for 12-month outcome: We conducted intent-to-treat analyses of repeated measures including all participants with available data at baseline, 6-, or 12-months by using SAS software version 9.2 (SAS Institute). We used a model-based approach with unweighted data. Initial explorations of 3-level, random-effects logistic models using SAS PROC GLIMMIX for binary outcomes yielded unstable estimates for program-specific random effects.^{16, 17}

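### Networks may be given one shared condition, but every variance rule stops at the program; if programs were assigned jointly, standard errors are too small to the extent that outcomes correlate within a network

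*Combined protocol and SAP*

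**What the plan says.** Section 4.1 names the unit, or program, as the unit of randomisation. Section 4.2 then makes an exception for large networks: "we may assign common conditions to collaborating units to maintain network ties". The note that follows in Section 4.2, on staged eligibility, does not withdraw it. Section 8.1a deals with very large multi-agency networks and gives another rule: "we may randomize units within that network to preserve network ties". The same section allows an agency to have units in both conditions.

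The analysis has one level of clustering throughout:

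- Section 5 (Overview) plans SUDAAN estimates "taking into account clustering within programs and weighting".
- Appendix A4 says the 6-month analyses "accounted for clustering (clients within programs), weighting, and multiple imputations", and the 3-year endpoint analysis follows the 6-month strategy.
- The 12-month GEE uses an exchangeable correlation at program level, and the mixed model for continuous MCS-12 uses program random effects. The 3-year longitudinal sensitivity analysis does likewise.
- The power section defines the variance inflation factor and the ICC at unit level, and takes degrees of freedom as clusters minus 2 when the ICC exceeds zero.

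Nowhere is there a network or agency cluster, a network correlation, or a sensitivity analysis for joint assignment. The documents do not say whether the option was used; Appendix A1 refers to publications for the details of randomisation.

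**The concern.** When several programs receive one condition by a single draw, the block is the randomised unit, not the program. A program-clustered variance counts each program's own variation, including the part that comes from its network. It misses the covariance between programs of the same network that are placed in the same arm. If that covariance is positive, the comparison of Community Engagement and Planning (CEP) with Resources for Services (RS) is more variable than its reported standard error shows. Confidence intervals are then too narrow, and the type I error exceeds the nominal 5%.

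Some positive correlation is plausible, because Section 4.2 describes these units as collaborating and their ties as worth keeping. Blocks need not be small: Section 4.1 expects some agencies to have more than 10 to 15 units. Sections 4.2 and 8.1a imply different randomised clusters, and the variance rule is safe for only one of them.

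**Working it through.** **Inputs from the documents.** Two-sided alpha 0.05 ("assuming two-sided tests with significance level 0.05"); analytic N = 780 (Table 4, row "With further 20% expansion, final"); 80 to 100 programs planned (Table 5) and 95 randomised (Section 6); unit ICC 0.00 to 0.02; VIF = 1 + (m − 1) × ICC.

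**The plan's own figure.** The plan states that "the final study was designed to have a power of .80 with an alpha of .05 (two-sided) and ICC=.00-.02", for a "standardized effects size of .20-.22 or higher in comparing two means". Using MDE = (1.960 + 0.842) × √(4 × VIF / N):

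- ICC 0: 2.802 × √(4/780) = 0.201.
- ICC 0.02 with 80 programs: m = 780/80 = 9.75 and VIF = 1 + 8.75 × 0.02 = 1.175, so MDE = 0.201 × √1.175 = 0.218. With t on 78 degrees of freedom it is 0.220.

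Table 4 therefore reproduces, with programs as independent clusters. There is no arithmetic error in it.

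**Assumptions (not in the documents).** One network of k programs receives a common condition. Clients in different programs of that network have correlation ρ, from 0 to 0.02. The program ICC is 0.02, the top of the plan's range. Since ρ is a component of the program ICC, 0.02 is also its ceiling.

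**Formulas.** With J = 95, m = 780/95 = 8.21 and a share f = k/95 of programs in the block:

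- Program-level VIF = 1 + 7.21 × 0.02 = 1.144.
- VIF with joint assignment = 1.144 + f × m × (k − 1) × ρ.
- Reported/true SE = √(1.144 / VIF with joint assignment).
- Type I error = 2 × [1 − Φ(1.96 × SE ratio)].

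Example, k = 10 and ρ = 0.02: the added term is (10/95) × 8.21 × 9 × 0.02 = 0.156. The VIF is 1.300, the SE ratio √(1.144/1.300) = 0.938, and the type I error 6.6%.

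| Programs in one shared network | ρ | VIF | Reported/true SE | Type I error |
|---|---|---|---|---|
| any | 0 | 1.144 | 1.000 | 5.0% |
| 5 | 0.005 | 1.153 | 0.996 | 5.1% |
| 5 | 0.02 | 1.179 | 0.985 | 5.4% |
| 10 | 0.005 | 1.183 | 0.983 | 5.4% |
| 10 | 0.02 | 1.300 | 0.938 | 6.6% |
| 15 | 0.005 | 1.235 | 0.963 | 5.9% |
| 15 | 0.02 | 1.507 | 0.871 | 8.8% |

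**Check of the mechanism.** A simulation with 96 programs of 8 clients, a program-level SE and 4,000 runs agrees with the formula. With 25% of programs in blocks of 4, the SE ratio is 1.00 and rejection 5.1% at ρ = 0, and 0.95 and 6.1% at ρ = 0.02. These simulated shares test the formula; they are not a claim about the trial.

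**The case against.** The strongest reply is that the exception may never have been used. It is worded as a possibility, and it sits in proposal text that still speaks of 50 to 60 units, a figure later raised to 80 to 100. Later descriptions are at program level: Section 6 reports 95 programs randomised, and Appendix A4 defines intervention status by the client's program. The sentences in Sections 4.2 and 8.1a share one purpose and may be one rule loosely worded. Clustering was nearly absent in most analyses of the predecessor trial, the plan's ICC range includes zero, and adjustment for the baseline outcome and community may absorb some network variation.

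Most of this stands, and it limits the size of the point. A reader might infer that any shared assignment makes the standard errors too small. The documents do not support that, since at zero between-program correlation nothing is lost. A reader might also infer that network variation is missing from the standard error altogether. It is not: it already forms part of between-program variance, and only the covariance between programs is missed. Nor do the documents support supposing that half of all programs were in shared blocks, because the option is confined to large networks.

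What the reply does not remove is that current text permits an assignment that no variance rule in the plan covers, and that two current sections differ on the rule. Program-level descriptions elsewhere do not show that joint assignment was not used.

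**Conclusion.** The point holds conditionally. The plan permits joint assignment within networks, gives a different rule elsewhere, and clusters on program in every model. If programs were assigned jointly, standard errors are too small to the extent that outcomes correlate within the network. For one network the shortfall runs from negligible (5 programs, at most 1.5%) to material (15 programs at the ceiling correlation, about 13%, type I error 8.8%). These figures rest on one shared network, 8.2 clients per program, a program ICC at the top of the plan's range, and no reduction from covariates. Network correlation, block size and number of blocks are all assumed, so there is no single corrected figure. The documents do not show that the reported intervals are in fact too narrow.

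**What to change.** Reconcile Sections 4.2 and 8.1a so that both state the assignment rule actually used. State which programs, if any, were assigned jointly. For those, use the jointly assigned block as the cluster for standard errors and degrees of freedom in all outcome models; elsewhere keep the program.

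The work is one cluster identifier in the analysis file. With one block of 10 among 95 programs, clusters fall from 95 to 86 (95 − 10 + 1), and degrees of freedom on the plan's rule from 93 to 84. Under the assumptions above, intervals would widen by about 2 to 7% for that block (1/0.983 to 1/0.938), and by 0.4 to 1.5% for a block of 5.

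The real cost is less equal cluster sizes, which weakens an ordinary sandwich variance. A small-sample correction should therefore go with the change; the Bell-McCaffrey bias-reduction method is already named in Section 5 under sampling and nonresponse weights. If no joint assignment was made, one sentence saying so closes the point and no result changes.
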